6.1 Primary Objectives and Endpoints

- To demonstrate bioequivalence of the fixed combination of praziquantel tablets 600 mg as Cisticid® product compared to Biltricide® tablets 600 mg, given as single dose to 1200 mg, healthy volunteers in fasting state.
- Calculate the primary endpoints AUC0-t, AUC0-∞ and Cmax.

6.2 Secondary Objectives and Endpoints

- The secondary endpoints variable are volume of distribution Ke, half-life elimination, clearance, and median residence time all these parameters will be presented only for informative reasons for both medications.
- To compare the safety and tolerability of all the experimental treatments.

6.3 Overall Trial Design and Plan

This randomized, open-label, single dose, a 3-periods and 3-sequences crossover design with a 7-day wash-out period.

The bioequivalence will be evaluated with primary endpoints are AUC0-t, AUC0-∞ or Cmax for enantiomers and racemic mixture of praziquantel.

The subjects will be randomized to one of the 2 treatment in 3 periods, 3 sequences (see table below). Ten subjects will be randomized to each treatment sequence with a minimum proportion of 30% for each sex in each treatment sequence.

Sequence	Period 1	ut I	Period 2	ut -	Period 3
PRR	Cisticid [®]	h-o-l	Biltricide [®]	h-o-i	Biltricide [®]
RPR	Biltricide®	/asl per	Cisticid [®]	/as per	Biltricide [®]
RRP	Biltricide®		Biltricide [®]		Cisticid [®]

7 Sample Size

The sample size estimation is based on the CV intrasubject variability of praziquantel.

The sample size is determined by the variability currently available, these values are 60 to 50 and 35% for Cmax and AUC, respectively. With this information, praziquantel is considered as a drug highly variable. In a clinical investigation realized by Merck Serono by a phase 1 design the variability obtained was 34.5% for L-praziquantel, 34.5% for AUC and 52% for Cmax.

The sample size calculation was realized using the PPD functions recommended by European Medicines Agency (EMA).

Considerations

- The reference-scaled average bioequivalence is applicable only for Cmax, for ABC apply the c conventional bioequivalence limits
- If the CVintrasubject value is greater than 50% the bioequivalence limits will be 0.70-1.43

Several assumptions were considered, there are:

- The real mean of ratio test/reference for primary pharmacokinetic parameters.
- Cmax CVintra subject reference: 45-55%
- Cmax CVintra subject test: 45-55%
- AUC CVintra subject reference: 39.5%
- AUC CVintra subject test: 39.5%
- Alpha value: 0.05
- Power 80%
- Droup-out rate: 20%

CCL

With all these assumptions the sample size required is 48 healthy subjects are needed to obtain power greater of 80%, neverthless considering the 20% of rate droup-out the sample size needed to avoid this problem is 60 subjects.

The 60 subjects going to be randomized into 3 sequences for each treatment, for this reason 20 subject will be enrolled in each treatment sequences.

8 Overview of Planned Analyses

PK parameters will be performed using PPD

Statistical analysis will be performed using SAS 9.4.

Descriptive statistical methods will be used to summarize demographic characteristics, pharmacokinetics parameters and adverse events. After the data base closing

Individual plasma concentration-time will be tabulated and plotted. Primary pharmacokinetics parameters, AUC and Cmax, will be tabulated and plotted by subject. Likewise, differences and odd ratios for test/reference will be tabulated for each subject for those parameters. Plasma concentration - time graphs will be made using arithmetic and semi-logarithmic scale. All de calculations will be determinated in concordance with NOM-177-SSA1-2013

Bioequivalence test methodology will be perform using the next codes: PRC GLM DATA=PK CLASS SEQ SUBJ PER TRT; MODELLNPARAM=SEQ PRE TRT SUBJ(TRT)/DDFM=SATTERTH; LSMEANS TRT/ADJUST=T PDIFF CL ALPHA=0.01. TEST H=SEQ E=SUBJ(TRT); RUN; QUIT;

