The non-dose-proportionality observed after doubling the dose is a factor ~ 4 for L-PZQ and a factor ~ 3 for rac-PZQ. Assuming similar non-dose-proportionality at lower doses of 10 mg/kg, the expected C_{max} for L-PZQ analyte after a dose of 10 mg/kg is around 40 ng/mL for L-PZQ (range 9.5 to 144 ng/mL) and ~ 300 ng/mL (range of ~ 180 -700) for rac-PZQ. As the current LLOQ for the L-PZQ is 5 ng/mL, a mean C_{max} of 40 ng/mL is only 8 times higher than the LLOQ and does not comply with the LLOQ being $< 5\%$ of C_{max} . For the racemate PZQ the LLOQ of 10 ng/mL is for most subjects expected to be within the pre-specified range of less than 5% of C_{max} . Since the BE comparison is to be based on L-PZQ levels for the BE endpoint, a dose of 1200 mg (2 tablets) is recommended, if rac-PZQ had been used for the BE endpoint, a dose of 600 mg might have been compliant.

Choice of analyte.

Although the WHO recommendation states that the parent compound is considered to best reflect the biopharmaceutical quality of the product and should be used to assess bioequivalence, the EMA guideline states for compounds consisting of enantiomers the following:

Enantiomers

The use of achiral bioanalytical methods is generally acceptable. However, the individual enantiomers should be measured when all the following conditions are met:

- (1) the enantiomers exhibit different pharmacokinetics*
- (2) the enantiomers exhibit pronounced difference in pharmacodynamics*
- (3) the exposure (AUC) ratio of enantiomers is modified by a difference in the rate of absorption.*

The individual enantiomers should also be measured if the above conditions are fulfilled or are unknown. If one enantiomer is pharmacologically active and the other is inactive or has a low contribution to activity, it is sufficient to demonstrate bioequivalence for the active enantiomer.

It is known that the PK and PD of the individual enantiomers of PZQ is clearly different (30; 35). Whether the exposure ratio of the enantiomers is modified by a difference in the rate of absorption or a difference related to differential metabolism is currently unknown. However this would point to the measurement of both individual enantiomers. In addition the current consensus is that the L-PZQ is the active enantiomer against *S. mansoni* and *Japonicum* (23).

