All in all, after having received feedback from WHO PQP pinpointing the fact that a nonchiral method is only acceptable if it is known that the exposure ratio is not modified by a difference in the rate of absorption, combined with the different ratios in enantiomers seen after administration of 20 and 40 mg/kg to humans, it was decided to use an enantioselective method for this registration study and the PK parameters of L-PZQ as the primary endpoint. As the CV% for L-PZQ were observed as being much higher than for rac-PZQ this had consequences for the sample size determinations.

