7.5.2 Calculation of Pharmacokinetics Variables

The following non-compartmental PK parameters will be calculated from the individual plasma L PZQ and rac-PZQ concentration-time data obtained on Days 1,8 and 15, respectively, using commercial software Phoenix®/WinNonlin® (Version 6.3 or higher).

Table 7 Pharmacokinetic Parameters Derived from L PZQ and rac-PZQ Concentrations

| | |
|-----------|---|
| C_{max} | Maximum observed drug concentration. |
| t_{max} | Time of the maximum drug concentration. |

| | |
|------------------|--|
| t_{lag} | Time prior to the first measurable (non-zero) concentration; calculated as last time point at which the concentration is <LLOQ before the occurrence of the first quantifiable concentration |
| λ_z | Terminal rate constant. |
| $t_{1/2}$ | Terminal elimination half-life. |
| AUC_{0-t} | Area under the drug concentration-time curve from time zero to the time last measurable concentration. |
| $AUC_{0-\infty}$ | Area under the drug concentration-time curve from time zero extrapolated to infinity. |
| $\%AUC_{extra}$ | Percentage of $AUC_{0-\infty}$ obtained by extrapolation |
| $CL_{/f}$ | Apparent clearance |
| $V_{Z/f}$ | Apparent volume of distribution during terminal phase |

The bioanalytical assessment will be outsourced to a third party vendor under the responsibility of Merck. PK parameter estimation and generation of PK TLFs will be outsourced to a third party vendor under the responsibility of Merck. Statistical analysis of Praziquantel will be conducted by the **PPD** [REDACTED], according to their standard operating procedures and in accordance with the NOM-177-SSA1-2013 (28).

CCI [REDACTED]

[REDACTED]

Substance Code
Protocol Number

Praziquantel
MS 200585-0002

Short title Praziquantel Bioequivalence Study

CCI

8 Statistics

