8.3.1 Primary Endpoints

The primary endpoints are the PK parameters AUC_{0-t} and C_{max} for L-PZQ.

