8.3.2 Secondary Endpoints

- Additional pharmacokinetic parameters will be estimated: t_{max} , t_{lag} , $AUC_{0-\infty}$, AUC_{extra} , $t_{1/2}$, λZ , CL/f and Vz/f of L-PZQ and t_{max} , t_{lag} , AUC_{0-t} , $AUC_{0-\infty}$, AUC_{extra} , C_{max} , $t_{1/2}$, λZ , CL/f and Vz/f parameters of rac-PZQ.
- To assess safety and tolerability of 1200 mg of the Cisticid tablets administered in fed condition. Safety will be assessed by AEs, standard laboratory parameters hematology, biochemistry, urinalysis, and coagulation), vital signs (body temperature, systolic blood pressure, diastolic blood pressure, and pulse rate) and 12-lead electrocardiogram (ECG) Analysis Sets

Table 8 Analysis Sets

For purposes of analysis, the following analysis sets are defined:

| Population | Description |
|-----------------|--|
| Enrolled | All participants who sign informed consent |
| Safety | The Safety Analysis Set will include all subjects who receive at least one dose of trial treatment. Subjects will be analyzed according to the actual treatment they receive. |
| Pharmacokinetic | All subjects that received all administrations of treatment and have PK parameters for AUC_{0-t} and C_{max} in all periods and without any relevant protocol violations and factors likely to affect the comparability of PK results. |

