8.4.2 Analysis of Primary Endpoints

The analysis of the primary endpoints AUC_{0-t} and C_{max} of L-PZQ will be performed using the PK population. For the demonstration of bioequivalence different approaches will be applied for AUC_{0-t} and C_{max} . For AUC_{0-t} the standard approach will be followed, i.e. the point estimate and the 90% CI of the Test/Reference geometric mean ratio must fall within [0.80, 1.25]. AUC_{0-t} of L-PZQ will be log-transformed and analyzed using a generalized linear model as given by the SAS code below:

```
PROC GLM DATA=PK;
```

```
CLASS SEQ SUBJ PER TRT;
```

```
MODEL LNPARAM = SEQ PER TRT SUBJ(TRT) / DDFM=SATTERTH;
```

LSMEANS TRT / ADJUST=T PDIFF CL ALPHA=0.10.

TEST H=SEQ E=SUBJ(TRT);

RUN;

QUIT;

The treatment difference TEST – REFERENCE will be estimated, and the 90% CIs for the difference in LS-means will be calculated. The difference and 90% CIs will be back-transformed to the original scale. If the 90% CI for the ratio (test/reference) lies entirely within the interval [80.00 – 125.00], then the BE criterion is fulfilled for AUC_{0-t} .

For the analysis of C_{max} , a reference-scaled bioequivalence approach will be applied as follows:

Point estimate and 90% confidence interval will be computed as described above for AUC. If $CV_{WR} \leq 30\%$ for C_{max} (i.e. the within-subject CV for the reference drug is $\leq 30\%$), then the common acceptance range for bioequivalence will apply. For $30\% < CV_{WR} \leq 50\%$ the acceptance interval will be widened according to $[U, L] = \exp [\pm k \cdot sWR]$, where U is the upper limit of the acceptance range, L is the lower limit of the acceptance range, k is the regulatory constant set to 0.760 and sWR is the intrasubject standard deviation of the log-transformed values of C_{max} of the reference product. sWR will be calculated using the data under reference treatment only. For all values of CV_{WR} greater than 50% the acceptance range is fixed to [69.84 – 143.19].

The geometric mean ratio for C_{max} should always lie within [80.00 – 125.00].

- a. Descriptive statistics and boxplots will be provided by treatment.

CCI

PROC GLM DATA=PK;

CLASS SEQ SUBJ PER TRT GROUP;

MODEL LNPARAM = SEQ PER TRT GROUP GROUP*TRT SUBJ(TRT) / DDFM=SATTERTH;

LSMEANS TRT / ADJUST=T PDIFF CL ALPHA=0.10.

TEST H=SEQ E=SUBJ(TRT);

RUN;

QUIT;

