8.4.3 Analysis of Secondary Endpoints

All secondary endpoints will be listed and descriptively analyzed.

There will be no formal statistical comparison of the secondary PK endpoints. Treatment ratio and 90% confidence interval will be presented for AUC_{0-∞} of L-PZQ and for all the secondary PK endpoints for rac-PZQ (t_{max}, t_{lag}, AUC_{0-t}, AUC_{0-∞}, AUC_{extra}, C_{max}, t_{1/2}, λ_Z, CL/f and V_Z/f). For t_{max} the Hodges-Lehmann shift estimate will be calculated together with the 90% confidence interval according to Tukey.

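### The SAP makes AUC0-∞ and the racemate primary, against the protocol's two L-PZQ endpoints, while declaring no changes

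*SAP*

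**What the plan says.** Protocol 8.3.1 begins "The primary endpoints are the PK parameters" and names only AUC0-t and Cmax of L-PZQ. The synopsis, 4.1 and 8.4.2 agree. Protocol 8.3.2 ("Additional pharmacokinetic parameters will be estimated") makes AUC0-∞ of L-PZQ secondary, together with all rac-PZQ parameters, including rac-PZQ AUC0-t, AUC0-∞ and Cmax. Protocol 8.4.3 adds "There will be no formal statistical comparison of the secondary PK endpoints", but does plan to show ratios with 90% confidence intervals for AUC0-∞ of L-PZQ and for the racemate.

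The analyte was a reasoned choice. After discussing regulatory feedback and enantiomer ratios that differed by dose, protocol 5.2 states that "it was decided to use an enantioselective method for this registration study and the PK parameters of L-PZQ as the primary endpoint".

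SAP 6.1 lists AUC0-t, AUC0-∞ and Cmax as primary, without naming an analyte. SAP 6.3 states "The bioequivalence will be evaluated with primary endpoints are AUC0-t, AUC0-∞ or Cmax for enantiomers and racemic mixture of praziquantel". SAP 8.1 puts AUC0-∞ beside AUC0-t under its AUC bioequivalence heading. SAP 15.2 concludes pharmacokinetic equivalence for both L-PZQ and the racemate. SAP 9 says the protocol's methods were adopted with no changes.

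**The concern.** Which endpoints carry the bioequivalence claim must be settled before the data are seen. The SAP moves secondary endpoints into the primary set, draws an equivalence conclusion from one group of them, and tells the reader that nothing moved. SAP 5 says its analyses will enter the study report and regulatory submissions, so the wrong status could be carried forward.

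Timing makes this worse. The protocol planned the trial for December 2017 to January 2018. SAP version 1.0 is dated May 2019, names 59 volunteers in its table titles and already states results.

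There is also a loose end in the decision rule. SAP 6.1 joins the endpoints with *and*, SAP 6.3 with *or*, and the SAP never says which endpoints must pass together.

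**Working it through.** **1. Endpoint status, side by side**

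| Item | Protocol | SAP |
|---|---|---|
| AUC0-t and Cmax of L-PZQ | Primary (8.3.1) | Primary (6.1, 6.3) |
| AUC0-∞ of L-PZQ | Secondary (8.3.2), ratio and 90% CI only (8.4.3) | Primary (6.1, 6.3); under bioequivalence for AUC (8.1) |
| AUC0-t, AUC0-∞ and Cmax of rac-PZQ | Secondary (8.3.2), ratio and 90% CI only (8.4.3) | Primary (6.3); equivalence concluded (15.2) |
| Second enantiomer | No parameters derived (7.5.2: "The following non-compartmental PK parameters will be calculated from the individual plasma L PZQ and rac-PZQ concentration-time data") | Included if the plural in 6.3 is literal |
| Lists of secondary parameters | Include AUC0-∞ and all rac-PZQ parameters | 6.2 and the end of 8.1 name neither AUC0-∞ nor any rac-PZQ AUC or Cmax (the extrapolated AUC in 8.1 is read as the extrapolated portion) |

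The promotion appears in several places, so it is more than one slip.

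**2. The plan's own sample size**

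Inputs from protocol 8.1: true ratio 0.95, AUC CV 39.5%, limits 0.80–1.25, one-sided alpha 0.05, power 80%, dropout 20%. For the three-sequence, three-period partial replicate design:

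- sw = √ln(1 + 0.395²) = 0.381
- SE = sw·√(1.5/N) = 0.381·√(1.5/48) = 0.0673
- df = 2N − 3 = 93, t = 1.661, expected half-width 1.661 × 0.0673 = 0.112 on the log scale
- Power, integrated over the chi-square distribution of the variance estimate: 80.5% at N = 48 and 77.9% at N = 45
- 48/(1 − 0.20) = 60

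The stated 48 and 60 reproduce.

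**3. Which decision rule that number fits**

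Cmax was simulated at subject level. Limits were exp(±0.76·sWR), fixed at 0.6984–1.4319 above a CV of 50%, with the point estimate kept within 0.80–1.25 (protocol 8.4.2; SAP 8.1 omits this last condition). The Cmax CV is 52% (protocol 8.1).

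| N | AUC0-t power | Cmax power |
|---|---|---|
| 30 | 57.5% | 81.4% |
| 48 | 80.5% | 95.6% |

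Across the planned Cmax CV range of 45–55%, Cmax alone reaches 80% with 30 to 33 subjects. Planning for 48 makes sense only if AUC must pass.

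**4. If all named endpoints must pass**

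The documents give no correlations, so these are assumed: 0.5–0.9 within subject between AUC and Cmax; 0.95–0.99 between AUC0-∞ and AUC0-t, with equal CVs.

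- Both L-PZQ primaries: 79–80% at N = 48, 86–88% at N = 59.
- With AUC0-∞ added: 75–79% at N = 48, 84–86% at N = 59.

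**5. If the *or* in SAP 6.3 were literal**

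At a true ratio of 0.80 for both metrics, Cmax passes while AUC0-t fails in about 36–38% of trials at N = 48 and 42–43% at N = 59. With Cmax CV 45% or 55% and correlation 0.7, the figures are 32% and 36% at N = 48, and 36% and 43% at N = 59. This is not an error in the Cmax test, because 0.80 lies inside the widened Cmax limits at that CV. It lies on the boundary for AUC0-t.

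**6. The racemate**

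No racemate CV is given, so no figure can be attached to that claim. Protocol 5.2 says only that the L-PZQ CV was much the higher of the two.

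**The case against.** The strongest reply is that the SAP is badly drafted rather than deliberately changed:

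- SAP 8 speaks only of AUC and Cmax as primary.
- SAP 15.4, headed as secondary analyses, also refers to racemate parameters.
- SAP 15.1, headed as primary analyses, lists AUC0-∞ but also Ke, which 6.2 calls secondary. Headings are therefore weak evidence of status.
- The plural enantiomers may echo the protocol's own discussion of measuring both, and the SAP's equivalence and parameter tables cover only L-PZQ and the racemate.
- References to metformin and gliclazide suggest text carried over from another study. SAP 5 cites protocol section 9 for statistics, which is section 8 here, so a different protocol version cannot be excluded.
- The protocol sets a criterion for each parameter but never says in so many words that both must pass.
- The ratios and intervals were planned anyway.

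Much of this is fair. The *or* is probably loose wording, and the figures in step 5 describe a rule that was probably never intended. The joint rule clarifies the protocol rather than restoring words that the SAP dropped. But none of these passages returns AUC0-∞ or the racemate to secondary status. Presenting an interval is not the same as concluding equivalence from it, and careless drafting does not make the no-changes statement true.

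**Conclusion.** The concern holds and should be fixed. The SAP changes which endpoints are primary, adds an unplanned equivalence conclusion for the racemate, and denies any change.

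The practical reach is limited. SAP 15.2 reports every result within its range for both analytes, so the L-PZQ conclusion would probably stand; its tables are not in the copy reviewed, so this rests on the text alone. What changes is the status of AUC0-∞ and of the racemate claim: given its date and contents, this SAP cannot show that either was pre-specified as primary. Requiring AUC0-∞ to pass as well would cost at most a few points of power under the assumed correlations. The missing joint rule matters only if the *or* is taken literally.

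**What to change.** Issue a dated SAP addendum and carry it into the report, leaving version 1.0 as it stands. Record it where protocol 8.6 and SAP 10.1 require changes to be documented.

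1. State that the only primary endpoints are AUC0-t and Cmax of L-PZQ, and that bioequivalence is concluded only if both meet their criteria in protocol 8.4.2.
2. Make AUC0-∞ and all racemate results secondary and descriptive, with the ratios and 90% intervals planned in protocol 8.4.3.
3. Withdraw the racemate equivalence conclusion in SAP 15.2, or label it post hoc.
4. Replace the statement in SAP 9 with a list of the departures from the protocol.

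The cost is the addendum and some report wording, with no new data or analysis. SAP 6.1 and 6.3 also conflict with the protocol on feeding state and sex, and with the protocol and SAP 7 on number per sequence. Those are separate matters and the passages must be reconciled.

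### SAP 6.3 misstates the basis for the bioequivalence conclusion: it joins the parameters with *or* and adds AUC0-∞, enantiomers and racemate, against the protocol and SAP 6.1

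*SAP*

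**What the plan says.** **Protocol.** Section 8.3.1: "The primary endpoints are the PK parameters AUC_{0-t} and C_{max} for L-PZQ". Section 8.3.2 lists AUC0-∞ of L-PZQ and every rac-PZQ parameter as secondary, and 8.4.3 plans no formal comparison for them. In 8.4.2, under the demonstration of bioequivalence, the AUC0-t rule is that "the point estimate and the 90% CI of the Test/Reference geometric mean ratio must fall within [0.80, 1.25". Cmax has its own scaled limits plus a constraint on the ratio. The AUC paragraph ends per parameter: if the interval lies inside the limits, "then the BE criterion is fulfilled for" AUC0-t. Section 4.3 states a single null and a single alternative, without parameters or margins.

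**SAP.** Section 6.1: "Calculate the primary endpoints AUC0-t, AUC0-∞ and Cmax". Section 6.3: "The bioequivalence will be evaluated with primary endpoints are AUC0-t, AUC0-∞ or Cmax for enantiomers and racemic mixture of praziquantel". Section 8.1 (headed Interim Analysis) has one block for AUC and one for Cmax and does not combine them. Section 9 says the protocol's methods were adopted and nothing was changed.

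**The concern.** With two primary parameters, testing each at one-sided 5% keeps the overall error at or below 5% only if both must pass. If either may pass, the chance of a wrong declaration is at least the chance that the easier parameter passes. Here that parameter is Cmax, whose limits can widen to 69.84–143.19.

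SAP 6.3 is the sentence that says what bioequivalence will be evaluated on. It uses *or*, and it draws the parameters from a wider pool than the protocol allows: AUC0-∞, the enantiomers (the protocol derives parameters only for L-PZQ and rac-PZQ) and the racemate. SAP 15.2 goes on to state equivalence for both L-PZQ and the racemate. So the SAP does not state correctly which results count or how they combine, and no other sentence in either document gives the joint rule outright.

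**Working it through.** **1. Inputs.** From protocol 8.1: true ratio 0.95, AUC CV 39.5%, Cmax CV 45–55% (52% observed for L-PZQ), one-sided alpha 0.05, power 80%, dropout 20%. From 5.1: three-period partial replicate with three sequences. From 8.4.2: limits 0.80–1.25 for AUC0-t; for Cmax, exp(±0.760·sWR) when CVwR is 30–50%, the fixed range 69.84–143.19 above 50%, and a ratio within 80–125. The correlation between the AUC and Cmax estimates is not given, so 0, 0.5 and 0.8 were assumed.

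**2. The plan's own sample size.**
- sW = √ln(1 + 0.395²) = √0.1450 = 0.381
- SE = sW·√(1.5/n) = 0.381·√(1.5/48) = 0.0673, with df = 2·48 − 3 = 93
- Power of the two one-sided tests is 0.805 at n = 48 and 0.779 at n = 45, so 48 is the smallest balanced number
- 48/(1 − 0.20) = 60 randomized

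Both stated figures reproduce, and they come from AUC alone. Cmax alone would need only about 30–33 subjects for 80% power.

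**3. AUC truly at its limit.** Simulation of 200,000 trials, n = 48, true AUC ratio 0.80, true Cmax ratio 0.95, correlation 0.5:

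| Cmax CV | AUC passes | Cmax passes | Both pass | Either passes |
|---|---|---|---|---|
| 45% | 0.050 | 0.964 | 0.049 | 0.964 |
| 52% | 0.050 | 0.958 | 0.049 | 0.959 |
| 55% | 0.050 | 0.948 | 0.048 | 0.949 |

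Check at 52%: P(either) = P(AUC) + P(Cmax) − P(both) = 0.0497 + 0.9576 − 0.0488 = 0.9585.

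The correlation hardly matters here. P(either) cannot fall below P(Cmax) = 0.958, and under independence it is 0.0497 + 0.9576 − 0.0497·0.9576 = 0.960. P(both) cannot exceed P(AUC) = 0.050.

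**4. The reverse case.** With a true AUC ratio of 0.95 and Cmax at its lower limit of 0.698 (Cmax CV 52%, correlation 0.5), bioequivalence is declared in about 81% of trials if either may pass and in 3.6% if both must.

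**5. Power when both must pass.** n = 48, both true ratios 0.95:

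| Cmax CV | Corr. 0 | Corr. 0.5 | Corr. 0.8 |
|---|---|---|---|
| 45% | 0.776 | 0.789 | 0.800 |
| 52% | 0.771 | 0.786 | 0.800 |
| 55% | 0.763 | 0.781 | 0.797 |

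Joint power is therefore about 0.76–0.80. The stated 80% is for AUC alone.

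**6. The passages side by side.**

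| Place | Parameters | Joined by |
|---|---|---|
| Protocol 4.1, 8.3.1 | AUC0-t, Cmax; L-PZQ | *and* |
| SAP 6.1 | AUC0-t, AUC0-∞, Cmax; analyte not named | *and* |
| SAP 6.3 | AUC0-t, AUC0-∞, Cmax; enantiomers and racemate | *or* |

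SAP 6.3 departs from the protocol in both columns. SAP 6.1 departs in one, by adding AUC0-∞.

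**The case against.** A reader might infer that the plan as written lets bioequivalence be declared on Cmax while AUC fails. The documents read together do not support that:

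- Protocol 8.4.2 and the synopsis make the AUC0-t criterion mandatory, so a product that fails it fails a stated condition.
- The protocol joins the two endpoints with *and* and tests one overall hypothesis. SAP 6.1 also uses *and*, although that line is about calculating the endpoints.
- Protocol 3, 5.2 and 8.1 say that the unscaled AUC limits drive the sample size, and SAP section 7 repeats the 48. Under an either-may-pass rule the easier parameter would set the number, and about 30–33 subjects would do.
- SAP 6.3 is an ungrammatical line in a design overview. It says what is evaluated, not when bioequivalence is concluded.
- SAP 15.2 describes all results as lying within their ranges, so nothing shows that an either-or rule was used.
- SAP section 9 adopts the protocol's methods, which can be read as letting the protocol override a stray word.

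All of this stands, and it limits the point to a correction of wording. It does not remove the contradiction. The SAP's evaluation sentence disagrees with the protocol on both the parameters and how they are joined, and the reader must infer the pivotal rule from several places.

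**Conclusion.** SAP 6.3 is wrong as written. It contradicts protocol 8.3.1 and 8.4.2 and SAP 6.1, and the no-change statement in SAP section 9 is inaccurate on this point. The protocol's intent that both L-PZQ parameters must pass can be recovered, but it is not stated in one sentence anywhere.

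The figures of about 96% against about 5% measure only what a literal *or* would do. They assume 48 evaluable subjects, CVs of 39.5% and 52%, true ratios of 0.80 (AUC) and 0.95 (Cmax), and a correlation of 0.5, to which they are insensitive. They do not estimate the error rate of the trial as the protocol describes it, and they do not show that the protocol allows bioequivalence on Cmax alone. The severity is that of a wording correction to the decision rule.

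**What to change.** - **SAP 6.3:** replace the sentence so that bioequivalence is evaluated on L-PZQ AUC0-t and L-PZQ Cmax. Treat AUC0-∞ and all rac-PZQ parameters as secondary, as in protocol 8.3.2, and remove AUC0-∞ from the primary list in SAP 6.1.
- **SAP 8.1 and protocol 8.4.2:** add *Bioequivalence is concluded only if L-PZQ AUC0-t and L-PZQ Cmax both meet their criteria.*
- **SAP section 9:** record this as alignment with the protocol. The SAP is dated May 2019 and already carries results text, so the correction should be dated.

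The cost is one added sentence in each document and the edits to SAP 6.1, 6.3 and 9. Requiring both to pass needs no alpha adjustment and no change to the 48 or 60 subjects. It would be accurate to note that the 80% power refers to AUC alone and that joint power is about 0.76–0.80, depending on the Cmax CV and the assumed correlation.
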